#### 12.2 Sample Size

Due to the low expected toxicity, a maximum of 18 patients will be enrolled during component 1. Based on the simulations from table 1, this should be sufficient and safe to define the MTD for component 1. Based on the simulations from table 2, component 2 should also be sufficient and safe to define the MTD. Enrollment will most likely include 12 patients under each component but could range from 2 to 18 patients. With expected enrollment of 12-18 patients/year, accrual for each component should be complete within 1.5 years. So after combining both trials, accrual should be complete in 2.5-3 years.

	Expected DLT			Excessive DLT			
Cells/	True	Probability of	Patient	True	Probability of	Patient	
dose	Probability	dose	Number	Probability	selecting dose	Number	
9x10 	1%	0%	3	10%	15%	6	
3x10 	3%	0%	3	25%	51%	6	
9x10 	6%	100%	6	40%	34%	6	

 Table 1. Operating characteristics for CRM (component 1)

	Expected DLT			Excessive DLT			
Cells/	True	Probability of	Patient	True	Probability of	Patient	
dose	Probability	dose	Number	Probability	selecting dose	Number	
3x10 	5%	0%	6	25%	74%	6	
9x10 	10%	100%	6	40%	26%	6	

Table 2. Operating characteristics for onthe (intery section). component 2
--

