Enrollment Plan:	Component 1: a maximum of 18 patients, but most likely 12 if toxicity is as expected Component 2: a maximum of 18 patients, but most likely 12 if toxicity is as expected
Accrual:	It is expected 12-18 patients could be enrolled per year with two sites.

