# NOTE: Component 2 may not begin until after the FDA gives permission to proceed (refer to Section 6.3).

Component 2 will use a similar design but identifies the MTD of FT596 when given as a single dose at Day 7 post-transplant. Up to two dose levels of FT596 are planned (one dose level below the MTD from Component 1 and the MTD from Component 1). Any two sequential dose levels of FT596 may be included: Dose Level -1:  $3x10^7$  cells/dose, Dose Level 1:  $9x10^7$  cells/dose, Dose Level 2:  $3x10^8$ cells/dose, Dose Level 3:  $9x10^8$  cells/dose.

The maximum tolerated dose will be determined by using a modified continual reassessment method (CRM). Patients are enrolled in cohorts of 3 starting at one dose level below the MTD of Component 1 (MTD-1). Only the MTD-1 and the MTD of Component 1 will be tested. A minimum of 28 days will separate each cohort. For the 1st cohort a minimum of 28 days will separate each patient to assess for dose limiting toxicity (DLT). In subsequent cohorts, the 1st and 2nd patient will be separated by at least 28 days and at least 14 days will separate the 2nd and 3rd patient. Each new cohort of three patients will be sequentially assigned to the most appropriate dose based on the updated toxicity probabilities. The MTD will be identified when the total sample size of 18 is exhausted or 6 patients are sequentially enrolled at the same dose.

Definitions of dose limiting toxicity and monitoring for excessive toxicity are found in Section 12. 4.

Follow-up (all patients): Direct study participation ends at 1 year post-transplant.

**Long-Term Follow-Up (any patient who received at least one dose of FT596):** After 1 year, follow-up will transfer to a separate long-term follow-up (LTFU) study (UMN CPRC #2020LS052) to continue the FDA's required 15 year follow-up after treatment with a genetically modified cell therapy. Participation in the LTFU study is mandatory as part of the inclusion criteria of this treatment study.

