The MTD will be determined by using a modified Continual Reassessment Method (CRM). (Goodman 1995) The CRM uses a power model for the probability of DLT at each dose, where the probability of toxicity at dose i is modeled as  $piexp(\alpha)$  where pi is a constant and  $\alpha$  is distributed a priori as a normal random variable with mean 0 and variance 2. The goal of this CRM will be to identify one of the 3 dose levels corresponding to the desired maximum acceptable toxicity rate of ≤25%.

Initial estimates of toxicity or the "skeleton" estimates are provided by the clinician. The initial estimates or prior probability of toxicity are listed as 1%, 3%, and 6% for doses 1, 2 and 3, respectively. As the study progresses, the CRM will continually update the estimates of the toxicity probabilities.

Patients are enrolled in cohorts of 3 starting at Dose Level 1. A minimum of 28 days will separate each cohort. For Dose Level 1 a minimum of 28 days will separate each patient to assess for dose limiting toxicity (DLT). In subsequent cohorts, the 1st and 2nd patient will be separated by at least 28 days and at least 14 days will separate the 2nd and 3rd patient. Enrollment will continue in cohorts of 3 and each new cohort of 3 will be sequentially assigned to the most appropriate dose based on the updated toxicity probabilities after the 3rd patient from the previous cohort has reached 28 days. The MTD will be identified when the total sample size of 18 is exhausted or 6 patients are sequentially enrolled at the same dose. A maximum of 18 patients is used in part due to low expected toxicity. The function 'crm' from the R package 'dfcrm' will calculate posterior means of toxicity probabilities. The CRM uses a Bayesian framework that combines experience from patients in the earlier part of the trial with the clinician's initial best estimate of the toxicity rates at each dose level to estimate a dose level that best corresponds to the target toxicity of ≤25%. Dose escalation of more than one level is not permitted with this design.

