Component 2 will use a similar design but identify the MTD of FT596 when given as a single dose at Day 7. Up to two dose levels of FT596 are planned (1 Dose Level below the MTD from component 1 and the MTD from component 1) so any two sequential dose levels of the following may be included (Dose Level -1:  $3x10^7$  cells/dose, Dose Level 1:  $9x10^7$  cells/dose, Dose Level 2:  $3x10^8$  cells/dose, Dose Level 3:  $9x10^8$  cells/dose).

The DLT events for Component 2 are the same as in Component 1 except for the addition of:

• Non-engraftment by Day 28 post-transplant

The MTD will be identified in the same fashion as Component 1 except that the initial estimates or prior probability of toxicity may be slightly higher due to the infusion of cells at Day 7 plus the additional possible DLT event. Assuming that we start at Dose Level 2, the skeleton probabilities might be listed as 5% and 10% for doses 2 and 3, respectively. The target toxicity level will still be  $\leq 25\%$ . As in Component 1, the CRM will continually update the estimates of the toxicity probabilities of both doses; first at the end of 28 days post infusion for each of the first three patients; and at the end of the of 28 day follow-up for the last patient in each of the 3 patient cohorts beyond the initial 3 patients. A minimum of 28 days will separate each patient in the 1st cohort to assess for dose limiting toxicity (DLT). In subsequent cohorts, the 1st and 2nd patient will be separated by at least 28 days and at least 14 days will separate the 2nd and 3rd patient.

As in Component 1, each new cohort of three patients will be sequentially assigned to the most appropriate dose based on the updated toxicity probabilities, and the MTD will be identified when a total sample size of 18 is exhausted or 6 patients are sequentially enrolled at the same dose.

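### Component 2 tests two doses, so the stated stopping rule makes 9 patients, not 12, its most likely size, and the Expected column of Table 2 does not follow from that rule

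*Combined protocol and SAP*

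**What the plan says.** Section 12.2 forecasts enrolment for both components together: "Enrollment will most likely include 12 patients under each component", with a stated range of 2 to 18. The Synopsis (Enrollment Plan) gives the same figure separately for each component: "a maximum of 18 patients, but most likely 12 if toxicity is as expected".

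Section 3 limits Component 2 to two doses, starting at the lower: "Only the MTD-1 and the MTD of Component 1 will be tested". Section 12.1 assigns patients in cohorts of three and ends the component by this rule: "the MTD will be identified when a total sample size of 18 is exhausted or 6 patients are sequentially enrolled at the same dose". For the Component 2 model it offers an example: "the skeleton probabilities might be listed as 5% and 10% for doses 2 and 3, respectively".

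Table 2 in Section 12.2 uses true DLT rates of 5% and 10% as its Expected scenario. It shows 6 patients at each dose, with the lower dose selected in 0% of trials and the upper in 100%. The text relies on it: "Based on the simulations from table 2, component 2 should also be sufficient and safe to define the MTD".

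**The concern.** The figure of 12 fits a design with three doses. Component 2 has two, under the same cohort size and stopping rule, so its most likely size should be one cohort smaller. The 6/6 split in Table 2 adds up to 12 but does not look like an outcome the rule can produce.

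Two things are at stake. One is the planned size and duration of Component 2. The other is whether Table 2 describes the design that will be run, since it is the stated support for Component 2. A reader of Table 2 would expect 6 patients at the lower dose; under the rule the usual number is 3.

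**Working it through.** **Inputs.** Section 12.1: power model with a normal prior (mean 0, variance 2), target 25%, cohorts of 3, no skipping of doses when escalating, stop at 6 consecutive patients on one dose or at 18; skeletons 1/3/6% (Component 1) and 5/10% (Component 2, illustrative). Section 12.2: true rates from Tables 1 and 2. All DLT outcomes were enumerated exactly, so there is no simulation error.

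The text leaves some choices open, so 16 readings were run with the stopping rule on:

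- plug-in or posterior-mean estimates;
- the dose nearest 25%, or the highest dose at or below 25%;
- stopping at 6 literally, or only if the CRM also recommends staying at that dose (confirmed);
- the MTD as the dose holding the six patients, or as the final CRM recommendation.

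**Control: Component 1.** Without DLTs the path is 3+3+6 = 12. At 1/3/6%, N = 12 occurs in 87.5–96.7% of trials, with median split 3/3/6. The stated 12 and the Table 1 Expected patient numbers are reproduced.

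**Component 2, literal rule.** Let L be a cohort at the lower dose and H a cohort at the upper dose. The possible paths, with probabilities at 5%/10% under nearest-dose assignment, are:

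| Path | N | Lower/upper | Probability |
|---|---|---|---|
| L L | 6 | 6/0 | 14.3% |
| L H H | 9 | 3/6 | 83.3% |
| L H L L | 12 | 9/3 | 0.4% |
| L H L H H | 15 | 6/9 | 1.9% |
| L H L H L, then one more cohort | 18 | 12/6 or 9/9 | 0.1% |

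N = 12 arises only as 9/3, so 6/6 is not a possible end state. The main entries can be checked by hand. The CRM escalates after 0/3 DLTs at the lower dose and then stays at the upper dose after 0 or 1 DLT in 3:

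- P(0/3 at 5%) = 0.95³ = 0.857, so P(N = 6) = 1 − 0.857 = 0.143.
- P(at most 1/3 at 10%) = 0.9³ + 3 × 0.1 × 0.9² = 0.729 + 0.243 = 0.972.
- P(N = 9) = 0.857 × 0.972 = 0.833.

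**Component 2, all readings with the rule on.**

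| | Literal | Confirmed |
|---|---|---|
| P(N = 9) | 83.3% | 75.9–82.7% |
| P(N = 12) | 0.4–2.4% | 0.7–11.5% |
| P(6/6 split) | 0 | at most 11.2% |
| Mean N | 8.6–8.7 | 9.4–9.7 |

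The lower dose has mean 3.5–3.9 patients and median 3 (printed: 6). The upper dose is selected in 78–97% of trials (printed: 100%). The reading closest to Section 12.1 (posterior means, nearest dose, final CRM recommendation) gives 3.5/5.2 patients and 3.9/96.1% selection literally, or 3.6/5.9 and 3.5/96.5% confirmed.

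**Other designs tried for Table 2 Expected, cohorts of 3.** With early stopping off at 18, mean patients are 3.8–4.7/13.3–14.2 and upper-dose selection is 96.3–99.1%. With a fixed 12, mean patients are 3.7–4.4/7.7–8.3, and 6/6 occurs in 7–14% of trials.

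**Sensitivity.** Skeletons of 1/3, 3/6, 8/15 and 10/20% keep 9 as the most likely size at true 5/10% (75.9–83.3%). At true 10/20% it is still 9 (65.3% literal, 47.8–62.1% confirmed), and at 15/25% it is 9 literally (51.8%). At 20/30% the literal mode becomes 6 (48.8% against 40.1% for 9), and at 25/40% it is 6 (57.8%). With the rule on, 12 was not the most likely size in any case tested.

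**Excessive columns.** With the rule on, the mean totals are 10.0–14.9 for Table 1 (printed patients sum to 18) and 7.7–10.2 for Table 2 (printed sum 12). With early stopping off (plug-in, nearest dose), Table 1 gives 6.47/5.65/5.88, which rounds to the printed 6/6/6, and Table 2 selection is 74.6/25.4% against the printed 74/26%. Table 1 Expected would then be 3/3/12 rather than 3/3/6. No single setting tested reproduces all four columns. The printed 74/26% is also close to some readings with the rule on (for example 75.6/24.4%), so it is not shown to be wrong.

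**Calendar.** The first cohort needs at least 3 × 28 = 84 days and each later cohort 28 + 14 + 28 = 70. Nine patients take at least 84 + 2 × 70 = 224 days; twelve take 84 + 3 × 70 = 294.

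**The case against.** The figure is a hedged forecast. The plan says most likely, gives a range of 2 to 18, and is bound only by the cap and the stopping rule. Nine lies inside that range, the error is on the long side, and both 224 and 294 days fit the plan's allowance of 1.5 years per component. No dose decision or analysis uses the 12. All of this stands, and it limits the consequence. It does not make 12 the most likely size.

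Table 2 is weaker evidence than the prose. Its caption and a column header are damaged in the text available, *Patient Number* is not defined, and the number of simulated trials is not given. With early stopping off, exact upper-dose selection reaches 99.1%, so a small simulation could print 100%; the selection cells alone prove little. The patient numbers are the real discrepancy, and they should be checked against the PDF. The prose figure in Section 12.2 and the Synopsis is intact and does not depend on the table.

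One design does give 6/6: cohorts of 6 with a fixed total of 12, where Expected selection is 1.5/98.5%. It contradicts both the stated cohort size and the stopping rule, and its Excessive selection is 60.7/39.3%, not the printed 74/26%.

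The enumeration also simplifies. It updates the model once per cohort, whereas Section 12.1 updates after each of the first three patients in Component 2. It leaves out the Section 12.4 halts and Dose Level -1. The exact percentages carry that caveat, but none of these features turns the two-dose path into 12.

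**Conclusion.** The concern holds. If toxicity is as expected, the most likely size of Component 2 under the stated rule is 9: probability 83.3% literally and 75.9–82.7% with confirmation, against at most 11.5% for 12. The stated 12 is correct for Component 1 only.

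The 6/6 patient numbers in Table 2 Expected are not reproduced by any setting tested with the stated cohorts of 3, subject to checking the cells in the PDF. The statement that Component 2 is sufficient and safe is not shown to be false, but it cites a table whose Expected column does not follow from Section 12.1.

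The size of the error is one cohort: 3 patients and at least 294 − 224 = 70 days of staggered enrolment. The percentages assume the illustrative 5/10% rates. The conclusion is insensitive to the skeleton and persists at true rates of 10/20%. Confidence is high for the Component 2 size and Table 2 Expected; no such claim is made for the Excessive columns.

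**What to change.** - In Section 12.2 and the Synopsis, give 9 as the most likely size of Component 2 if toxicity is as expected. Keep 12 for Component 1 and the maximum of 18 for both.
- Rerun Tables 1 and 2 under one common setting with the Section 12.1 stopping rule on, and replace both.
- State with the tables how a dose is assigned (nearest to 25%, or highest at or below 25%), how the MTD is read at stopping (dose holding the six patients, or final CRM recommendation), whether stopping requires the CRM to stay at the dose, what *Patient Number* means, and how many trials were simulated.
- Check that the sufficient-and-safe statement still agrees with the rerun.

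The cost is two number edits, a short simulation, two replacement tables and a few sentences. It needs no extra patients and changes no clinical rule.

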#### **12.3 Statistical Analysis**

The MTD will be determined in Component 1 and Component 2 per the design. All other endpoints including safety, progression-free survival, relapse, non-relapse mortality, toxicity rates and other clinical activity will be estimated descriptively. This will include simple frequencies, proportions, means, standard deviations/standard errors, medians and ranges.

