#### 1.2 Secondary Objectives

- To evaluate the adverse events related to FT596 administered post auto-HSCT in combination with rituximab (Rituxan or an FDA approved biosimilar, e.g. Truxima and Ruxience).
- To determine preliminary efficacy based on progression free survival (PFS) and relapse/progression at 12 months post auto-HSCT.
- To determine the incidence of non-relapse mortality at 100 days and 1 year post auto-HSCT.

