#### 6.7 Duration of Study Participation

Follow-up for disease and survival endpoints continues through 1 year post-transplant.

Direct study participation ends approximately 30 days after the last FT596 infusion and once an End of Treatment visit has occurred.

Clinical information including disease status and potential late toxicities associated with FT596 will be abstracted from follow-up visits associated with the transplant at Day 100, Day 180, Day 270 (if done), and Day 365. After Day 365 (1 year), the patient's follow-up will transfer to a designated long-term follow-up protocol per Section 6.8.

Rituximab or the FDA approved biosimilar may continue (independent of this study) per institutional practice.

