### 8 Schedule of Treatment, Tests, and Procedures

If a patient is consented after the transplant procedure, initial inclusion and exclusion criteria is abstracted for the standard of care assessment prior to transplant as permitted in the patient consent form document. No research related procedures or sample collections are permitted prior to consent signing.

For scheduling purposes, the rituximab/FT596 "package" is administered with a +3 day window from the targeted FT596 administration day (Day 30 or Day 7 post-transplant). Rituximab or an FDA approved biosimilar is given 2 to 3 days (48 to 72 hours) prior to the planned FT596 infusion.

In the event of rituximab related toxicity, the FT596 infusion may delayed for up to 7 days to permit resolution of any related adverse events to Grade 1 or better.

A  $\pm$  1 Day window is permitted for visits through the End of Treatment (EOT) visit; however, whenever feasible do not shift subsequent time points off of the targeted day (based on the actual day of the FT596 infusion).

After the EOT visit, follow-up for this study will coincide with the standard of care transplant follow-up schedule through 1 year post-transplant.

In addition, targeted days may be altered as clinically appropriate.

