#### **12 Statistical Considerations**

#### 12.1 Study Designs

This study consists of two components. The 1st component is a Phase I clinical trial to identify the maximum tolerated dose (MTD) of FT596 at Day 30 post FT596 infusion. The second component is a Phase I clinical trial to identify the MTD of FT596 at Day 7 post FT596 infusion. Rituximab is given 2-3 days before FT596. In addition to identifying the MTD and providing preliminary estimates of safety, secondary objectives include providing preliminary descriptive estimates of efficacy such as progression-free survival, relapse and non-relapse mortality along with their error measurements. Correlative objectives include measurement of the persistence of FT596 in blood after each FT596 infusion by immunophenotyping and PCR up to 1 year, the association of FT596 persistence with safety and anti-tumor activity.

Component 1 will identify the MTD of FT596 when given as a single dose at Day 30. Up to three FT596 dose levels are planned (Dose Level 1:  $9x10^7$  cells/dose, Dose Level 2:  $3x10^8$  cells/dose, Dose Level 3:  $9x10^8$  cells/dose with a Dose Level - 1:  $3x10^7$  cells/dose tested only if DLT at DL1).

**Component 1 dose limiting toxicity** is defined as any of the following events within 28 days after the FT596 dosing based on CTCAE v5:

- Grade 4 hematologic toxicity lasting > 7 days (not including lymphopenia)
- Grade 4 non-hematologic toxicity
- Grade ≥3 FT596 Infusion Related Reaction
- Grade 2 acute GVHD that requires steroid therapy >7 days or progression after 3 days of steroids or has partial response after 14 days of treatment
- Grade ≥3 acute GVHD
- Grade 4 cytokine release syndrome (CRS)
- Grade 3 CRS that does not resolve to < Grade 2 in 72 hours
- Grade 3 neurotoxicity

- Grade 3 organ toxicity involving vital organs; cardiac, central nervous system and pulmonary that lasts for longer than 7 days including Grade 3 Investigations (laboratory values) of any duration that indicate damage to vital organs.
- Any Grade 3 non-hematological toxicity that does not resolve to ≤Grade 2 within 72 hours; excepting Grade 3 renal and hepatic toxicity which may take up to 7 days to resolve to ≤Grade 2

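### Section 12.3 lists only simple proportions and standard errors for PFS, relapse, NRM and toxicity: these have no rule for incomplete follow-up and give an error of zero when no event occurs

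*Combined protocol and SAP*

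**What the plan says.** Section 1.2 makes these endpoints secondary objectives: "To determine preliminary efficacy based on progression free survival (PFS) and relapse/progression at 12 months post auto-HSCT" and "To determine the incidence of non-relapse mortality at 100 days and 1 year post auto-HSCT".

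Section 12.3 is the only analysis text for them: "All other endpoints including safety, progression-free survival, relapse, non-relapse mortality, toxicity rates and other clinical activity will be estimated descriptively". Its next sentence gives the content: "This will include simple frequencies, proportions, means, standard deviations/standard errors, medians and ranges". Section 12.1 promises preliminary estimates of "progression-free survival, relapse and non-relapse mortality along with their error measurements", without saying which error measure is meant. The statistical section names no Kaplan-Meier estimate, cumulative incidence, confidence interval, censoring rule or treatment of competing events.

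On follow-up, Section 6.7 states: "Follow-up for disease and survival endpoints continues through 1 year post-transplant". Section 8 adds that after the end-of-treatment visit "follow-up for this study will coincide with the standard of care transplant follow-up schedule through 1 year post-transplant". Appendix I leaves the timing of disease assessments to each institution's standard of care. Section 12.2 expects 12 patients per component, with a range of 2 to 18.

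**The concern.** PFS, relapse and NRM are times to events, and relapse and NRM compete. A proportion at a fixed time needs every patient's status at that time. The plan does not say what happens to a patient whose status at 12 months is unknown, or who is summarised before 12 months have passed. Counting that patient as event-free and leaving the patient out move the estimate in opposite directions.

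The second problem does not depend on follow-up. The only error measures listed are standard deviations and standard errors, and the standard error of an observed proportion of zero is zero. In a component of 12 to 18 patients, no NRM event by Day 100 or 1 year is a realistic outcome, and so is no event for a rare toxicity. A report of 0% with standard error 0 would look like certainty where the data still allow a substantial rate. Section 2.4 says that a multi-dose study would be proposed next if the treatment is found safe, so the precision of the safety estimates matters to a reader of the results.

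**Working it through.** The plan states no precision figure for these endpoints, so there is none to reproduce. The one plan figure used throughout is the sample size. The expected-toxicity scenario in Table 1 of Section 12.2 gives 3 + 3 + 6 = 12 patients for Component 1. A simulation of that CRM (skeleton 1%, 3%, 6%; prior variance 2; target 25%; cohorts of 3; stop at 6 in sequence on one dose or at 18 in total) gave a mean of 11.8 patients and exactly 12 with probability 0.96. So n = 12 reproduces for Component 1; n = 18 is the stated maximum.

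**Step 1: no events.** Standard error = sqrt(p(1-p)/n). With p = 0 this is 0 for every n. The upper limit of the exact two-sided 95% interval for 0 of n is 1 - 0.025^(1/n):

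- n = 12: 1 - 0.025^(1/12) = 26.5%
- n = 18: 1 - 0.025^(1/18) = 18.5%

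The probability of seeing no event is (1 - q)^n for a true rate q. The documents give no expected NRM, so 3%, 5% and 9% are assumptions. The 9% is the remainder from the registry figures in Section 2.2 for early-failure patients: 100 - 44 (PFS) - 47 (relapse/progression) = 9.

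| Assumed NRM | 0 of 12 | 0 of 18 |
|---|---|---|
| 3% | 0.69 | 0.58 |
| 5% | 0.54 | 0.40 |
| 9% | 0.32 | 0.18 |

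**Step 2: complete follow-up.** If every patient's status at the time point is known, the observed proportion is unbiased for 12-month PFS. For relapse and NRM it is the cumulative incidence: with true values of 47% and 9%, the crude proportions are 47.0% and 9.0%. Competition between the events adds no error. The error belongs to one minus Kaplan-Meier with the competing event censored, which under constant hazards would give 49.8% and 12.4%. The plan does not propose that method.

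**Step 3: incomplete follow-up.** Take a true 12-month PFS of 50% (the reference in Section 2.5), so the event hazard is a = -ln(0.5) per year. Let independent loss have hazard c = -ln(1 - L), where L is the assumed chance of loss by 12 months in the absence of an event. The share with an observed event is E = a/(a+c) x [1 - exp(-(a+c))]. The share lost first is C = c/(a+c) x [1 - exp(-(a+c))].

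For L = 20%: a = 0.693, c = 0.223, exp(-(a+c)) = 0.5 x 0.8 = 0.40. So E = 0.756 x 0.60 = 0.454 and C = 0.244 x 0.60 = 0.146. Counting lost patients as event-free gives 1 - 0.454 = 54.6%. Dropping them gives 1 - 0.454/(1 - 0.146) = 46.8%.

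| Assumed loss L | Lost counted event-free | Lost dropped |
|---|---|---|
| 0% | 50.0% | 50.0% |
| 5% | 51.1% | 49.3% |
| 10% | 52.3% | 48.5% |
| 20% | 54.6% | 46.8% |

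For relapse and NRM at 47% and 9%, 20% loss lowers the crude proportions to 42.8% and 8.2%.

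**Step 4: scale.** At n = 12 and PFS 50% the standard error is sqrt(0.5 x 0.5/12) = 14.4 points, and the exact 95% interval for 6/12 is 21.1% to 78.9%.

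**The case against.** The strongest reply is that this is a phase I study with descriptive secondary endpoints at fixed times, and that follow-up to those times is planned for every patient. Visits at 3, 6 and 12 months are scheduled, consent to a long-term follow-up study is an entry condition, deaths must be reported within 24 hours, and mortality by Day 100 is a stopping event. Loss before Day 100 is hard to assume. On this view a simple proportion is adequate, and any bias at plausible loss is small against the sampling error. All of this stands. It limits the bias argument but does not touch the zero-event result.

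Four stronger readings are tempting, and the documents do not support them:

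- A reader might infer that Section 12.3 prescribes proportions for PFS and NRM to the exclusion of other methods. The list is introduced as what the description will include, is pooled over all endpoint types, and assigns no statistic to any one endpoint.
- A reader might infer that proportions misstate relapse and NRM because the two compete. Step 2 shows that they do not when follow-up is complete.
- A reader might infer that loss is likely because late data come from routine visits. That bears on when disease is assessed; it is no evidence of drop-out, and the documents give no loss rate.
- A reader might infer that the PFS and NRM estimates will decide the follow-on study. Section 2.4 makes that step conditional on safety and ties it to no PFS or NRM figure.

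The reply also exposes a trap in the obvious remedy. Kaplan-Meier and cumulative incidence do not by themselves cure the zero-event problem: their usual variance is also zero with no events, and a log-log interval is then undefined.

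**Conclusion.** The point holds in limited form. As written, Section 12.3 supplies only simple summaries and standard errors, with no interval and no rule for patients not followed to the time point. Following it as it stands would report an error of zero for a plausible 0/12 or 0/18 result, where the exact upper limits are 26.5% and 18.5%. Those limits rest on arithmetic alone; how likely the result is rests on the assumed NRM rates.

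Bias in the PFS proportion is conditional. It is absent with complete follow-up, and about +1 to +5 or -1 to -3 points at an assumed 5-20% loss, depending on a counting rule that the plan does not state. These figures assume constant hazards and loss unrelated to outcome. They are well below the sampling error at n = 12. The CRM dose assignment, the MTD and the stopping guidelines in Section 12.4 do not use these summaries and are unaffected.

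**What to change.** In Section 12.3, replace the generic list for these endpoints with the following:

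- 12-month PFS by Kaplan-Meier with a log-log 95% confidence interval, censoring at the last disease assessment.
- Relapse/progression at 12 months, and NRM at 100 days and 1 year, by cumulative incidence, each treated as the competing event of the other, with 95% confidence intervals.
- Toxicity proportions with exact (Clopper-Pearson) 95% confidence intervals.
- When no event is observed for NRM or any other endpoint, the exact binomial 95% limit among patients followed to the time point, in place of a standard error.

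The last item is needed because the first two do not cover the zero-event case. The cost is a few sentences of analysis text. The same data and standard software serve, and no visits, patients or decision rules change.
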